4 STATISTICAL ANALYSIS

4.1 Sample Size Requirements

The sample size of 50 was chosen for 3 reasons:

1. This is an achievable sample size given the number of known pool of HCV/HIV coinfected liver transplant candidates and recipients at the participating study sites and the available time for recruitment. This sample size will also represent the largest experience with interferon- and ribavirin-free therapy in this specific population. In terms of the primary efficacy endpoint, combined (pre and post-transplant) and separate analyses of SVR₁₂ will be estimated. Table 1 shows the width of a 95% exact confidence interval for the probability of SVR₁₂ as a function of the number of SVRs in a sample size of 50. For instance, if all 50 subjects have sustained virologic response, we can be 95% confident that the true SVR probability is between 0.929 and 1.

Table 1: SVR₁₂ Confidence Interval Table

50	48	46	44	42	40
0.929-1	0.863-0.995	0.808-0.978	0.757-0.955	0.709-0.928	0.663-0.900

Exact 95% confidence interval if the number of SVRs out of 25 is as shown in row 1.

2. A sample size of 50 (pre and post-transplant) is sufficient to address the safety endpoints. If the true event probability is 5% or more, there is about a 92% chance of observing at least one such adverse event (Table 2). Consequently, if no one has a given type of AE, we can be confident that its true probability is under 5%. This trial will provide preliminary evidence on the safety and efficacy of FDC in pre or post liver transplant HIV/HCV coinfected subjects.

Table 2: Adverse Event Probability Table

.01	.05	.10	.15
39%	92%	99.5%	99.97%

For AE probabilities shown in row 1, row 2 gives the probabilities of observing at least 1 participant with the AE among 50 total participants.

3. A sample size of 50 is adequate to support the mechanistic virologic and immunologic studies.

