Furthermore, use of RBV in HIV/HCV coinfecte subjects is associated with an increased incidence of anemia that requires dose reductions, interruptions and or treatment with erythropoietin. All these increase the cost and adverse event profile of the therapeutic regimen. The development of a treatment regimen without PegIFN/RBV for genotype 1 patients co-infected with chronic HCV infection and HIV-1 infection would allow for increased access to successful treatment to a significant proportion of the HCV-infected population. Safety, tolerability and efficacy of IFN free regimens appear comparable between the HIV/HCV coinfecte and HCV monoinfected subjects supporting the evaluation of similar regimens to those under evaluation in HCV monoinfection. Furthermore, certain studies suggest that patients with a robust immune status respond better to HCV therapy [43].

Overall Risk/Benefit Assessment

The SOF/LDV FDC product combines a potent HCV nucleotide inhibitor and a potent HCV NS5A inhibitor, and has the potential to be a once-daily regimen for the treatment of chronic genotype 1 HCV infection.

The potential benefits of SOF/LDV FDC product for the treatment of chronic HCV are:

- Greater antiviral efficacy (i.e., rapid and durable eradication of HCV) compared to the current standard of care

- A reduction in the AEs currently associated with the use of PegIFN, RBV, and/or available protease inhibitors (telaprevir, boceprevir)
- Shortened duration of therapy
- Increased adherence to therapy with the convenience of a once daily, all oral, FDC

The combination of sofosbuvir 400 mg and ledipasvir 90 mg has been administered in studies to over 2,500 subjects. A review of the safety data from completed studies shows that treatment with sofosbuvir and ledipasvir or FDC has been generally well tolerated. No deaths or discontinuations of study drug due to AEs have been reported. No Grade 4 or clinically relevant Grade 3 laboratory abnormalities have been reported. No trends in vital sign changes have been observed following administration. The favorable safety and efficacy profiles of support further evaluation of this combination.

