3.0 STUDY DESCRIPTION

Approximately fifty HIV/HCV coinfecte patients with decompensated liver disease will be enrolled in the study. Ten (up to twenty) subjects will be treated with FDC SOF/LDV pre or post liver transplant and followed prospectively. Forty + subjects will be enrolled retrospectively with the intent to capture all patients who have been exposed to sofosbuvir based DAA therapies at participating sites since 1/2014, and to mirror the population being enrolled prospectively.

In addition, participants in the retrospective arm will be contacted to consent to one prospective study visit for liver staging to determine rates of reversal of decompensation, reversal of cirrhosis and improvements in graft survival post treatment, and for future contact by the NIH Clinical Center to assess longer term outcomes when this study ends.

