3.1 Retrospective Arm

Participating sites will collect clinical data on all of the HIV/HCV co-infected patients with decompensated liver disease (CPT >7 pre or post liver transplant) treated with sofosbuvir based DAA therapies since 1/2014 at their center. This will be done under IRB approved waiver of consent if possible so that all treated patients meeting the inclusion criteria can be included to avoid statistical bias. Data collected will mirror the data collected in the prospective arm. In addition, participants will be contacted to provide consent to return to the site for one visit for current liver staging to evaluate reversal of fibrosis (unless liver staging by Fibroscan or liver biopsy was done in the previous 12 months), and to be contacted in the future by the NIH Clinical Center for long term follow-up.

- Efficacy will be defined as HCV RNA undetectable \geq 12 weeks post end of sofosbuvir based DAA therapy.
- Safety and tolerability will be defined by
 - discontinuation rates
 - rates of hospitalization during DAA therapy
 - frequency of anemia requiring blood transfusion or EPO
 - survival.
- Reversal of decompensation: defined by CP score and MELD score at last follow-up (evaluated at time to event given the variability in length of follow-up post treatment)
- Reversal of fibrosis: defined by liver fibrosis by Fibroscan or biopsy at last follow-up (evaluated at time to event given the variability in length of follow-up post treatment)

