5 PATIENT POPULATIONS

5.1 Retrospective Arm Inclusion Criteria

The intent of the Retrospective Arm is to capture all HIV/HCV coinfected patients exposed to sofosbuvir based DAA therapy since 2014, to mirror the population enrolled in the Prospective Arm.

Liver transplant candidates (listed) and decompensated cirrhotics (not listed) for liver transplant

1. Treated with sofosbuvir based DAA for any duration since 2014
2. Age >18 years at time of treatment
3. Pre-treatment Child's Pugh score of 7 or greater
4. Pre-treatment laboratory MELD ≥ 6 and ≤ 30
5. Survived at least 12 weeks after start of treatment
6. HIV-positive on stable ART for at least 4 weeks pre-treatment
7. Chronic HCV infection with at least one measurement of plasma HCV RNA $\geq 1,000$ IU/mL prior to treatment with sofosbuvir based DAA therapy
8. HCV genotype 1, 4, 5 or 6

Liver transplant recipients

1. Treated with sofosbuvir based DAA post liver transplant for any duration since 2014
2. Liver transplant from 2000 to current
3. Age >18 years at time of treatment
4. Treated initiated at least 1 month post-liver transplant
5. Post-LT stage of liver disease documented within the prior year of treatment start date by standard of care methods of liver staging
6. Survived at least 12 weeks after start of treatment

7. HIV-positive on stable ART for at least 4 weeks pre-treatment
8. Chronic HCV infection with at least one measurement of plasma HCV RNA $\geq 1,000$ IU/mL prior to treatment with sofosbuvir based DAA therapy
9. Fibrosis staging done within 1 year of start of DAA therapy
10. HCV genotype 1, 4, 5 or 6

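### Section 4.1 presents all 50 patients as ribavirin-free and FDC evidence, but the design ensures this for only the 10 to 20 prospective patients, and no SVR12 estimate by regimen or ribavirin use is planned

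*Combined protocol and SAP*

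**What the plan says.** Section 4.1 opens with "The sample size of 50 was chosen for 3 reasons". Under the first reason it describes these 50 patients as the "largest experience with interferon- and ribavirin-free therapy" in this population. The second reason, on safety, closes by saying that the trial will give preliminary evidence on the safety and efficacy of the FDC.

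Section 3.0 shows how the 50 are made up:

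- Prospective: "Ten (up to twenty) subjects will be treated with FDC SOF/LDV pre or post liver transplant and followed prospectively".
- Retrospective: "Forty + subjects will be enrolled retrospectively with the intent to capture all patients who have been exposed to sofosbuvir based DAA therapies" at the participating sites since January 2014.

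Section 5.1 sets the regimen criterion for retrospective transplant candidates and unlisted decompensated patients: "Treated with sofosbuvir based DAA for any duration since 2014". The criterion for transplant recipients is the same apart from the post-transplant timing. Neither list excludes ribavirin or interferon.

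Section 2.1 separates the two therapies. Primary objective 1 concerns sofosbuvir-based DAA therapy, and primary objective 2 concerns SOF/LDV. Section 4 does not carry that separation through. SVR12 is to be estimated combined and separately before and after transplant (4.1), with an exact Clopper-Pearson interval (4.4.1). Current regimen and ribavirin are absent from the named sources of heterogeneity and from the exploratory covariates in 4.4.2.

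Section 3.1 lists "frequency of anemia requiring blood transfusion or EPO" and discontinuation rates among the retrospective safety measures. Section 1.1 says that ribavirin in coinfected patients "is associated with an increased incidence of anemia that requires dose reductions".

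**The concern.** Section 4.1 gives the whole sample a property that eligibility does not secure for most of it. The background in sections 1.0 and 1.1 describes sofosbuvir given with ribavirin before and after transplant, sofosbuvir within interferon-containing regimens, and SOF/LDV with or without ribavirin. The retrospective window opens in January 2014, while section 1.1 dates the approval of SOF/LDV to October 10, 2014. For roughly nine months of the window, patients treated outside trials would have had some other sofosbuvir regimen. That does not show how many took ribavirin, but it makes a mixed cohort a realistic prospect.

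Two results are affected if the plan is followed as written. The SVR12 rate will be a mixed-regimen rate, and so will the retrospective anemia rate, for an outcome that the protocol itself ties to ribavirin. Neither can support a statement about ribavirin-free therapy or about the FDC. Section 1.1 sets guidance on treatment strategies as the study's goal, and such guidance needs results by regimen.

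**Working it through.** **Inputs.** Total 50 (4.1). Prospective 10, up to 20, all on SOF/LDV (3.0). Retrospective 40 or more, any sofosbuvir-based regimen (3.0, 5.1). Exact two-sided 95% interval (4.4.1). The ribavirin share among retrospective patients is not given, so it is varied from 0 to 100%.

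**The plan's own figures.** When all n patients respond, the exact lower limit is 0.025^(1/n). For n = 50 this is 0.025^(1/50) = 0.929, as in Table 1. The other five entries of Table 1 also reproduce for n = 50 (for example, 40 responders give 0.663 to 0.900), although its footnote refers to 25. Table 2 uses 1 − (1 − p)^n. At p = 0.05 and n = 50 this is 1 − 0.95^50 = 0.923, against the stated 92%. The arithmetic for 50 patients is right.

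**What the design guarantees.** Only the prospective patients are certain to be on SOF/LDV without ribavirin. If all respond:

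- n = 10: lower limit 0.025^(1/10) = 0.692
- n = 20: lower limit 0.025^(1/20) = 0.832

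**Range over the unknown share.** With 10 prospective and 40 retrospective patients and a ribavirin share f among the latter, the ribavirin-free number is n = 10 + 40(1 − f).

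| Assumed share f | Ribavirin-free n | Lower limit if all respond | Chance of at least one event at a true rate of 5% |
|---|---|---|---|
| 0% | 50 | 0.929 | 92% |
| 25% | 40 | 0.912 | 87% |
| 50% | 30 | 0.884 | 79% |
| 75% | 20 | 0.832 | 64% |
| 100% | 10 | 0.692 | 40% |

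The same table serves for an FDC statement if f is read as the share of retrospective patients who did not receive SOF/LDV. The two shares need not agree, because a retrospective patient may have had SOF/LDV with ribavirin, or another sofosbuvir regimen without it. Splitting by SOF/LDV alone therefore does not isolate the ribavirin-free patients.

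**The case against.** The strongest reply is that no planned calculation is wrong. Table 1 is offered for the probability of SVR12 in a sample of 50 and is not labelled ribavirin-free. Objective 1 covers sofosbuvir-based therapy generally, the objectives already name SOF/LDV separately, and the disputed sentence can be read as a remark on feasibility and novelty. Section 4.4.2 also admits heterogeneity in open-ended terms, says that the sample is too small for extensive modelling, and defers efficacy details to a statistical analysis plan.

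Much of this stands, and it rules out several stronger readings that a reader might infer:

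- *That 0.929 is wrong.* It is correct for objective 1. It fails only when it is carried over to a ribavirin-free or FDC statement.
- *That anemia is pooled over all 50.* Anemia treated with transfusion or EPO is a retrospective-arm measure only (3.1, 10.6). The primary safety endpoint in 4.1.3 is permanent discontinuation because of an adverse event. Ribavirin users and non-users are mixed within the retrospective arm.
- *That regimen will not be collected.* The retrospective schedule in 11.2 has no row for it. But that schedule also has no row for hospitalization, transfusion or EPO, or death, which 10.6 says sites will record. The abstraction form is not among the documents, so capture is unconfirmed rather than absent.
- *That sofosbuvir plus ribavirin is known practice at these sites.* The background cites it from earlier studies only.

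The reply does not remove the mismatch. The sentences in 4.1 are about the sample of 50, eligibility does not secure the property they claim, and the documents specify no estimate by regimen or ribavirin use. A later analysis can make that split only if the field was abstracted.

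**Conclusion.** The point holds as one of labelling and reporting. By design 10 to 20 patients are ribavirin-free and on the FDC. In a sample of 10 plus 40, the ribavirin-free total could be anywhere from 10 to 50, with an all-responder lower limit anywhere from 0.692 to 0.929. No value in that range is more credible than another on these documents, and at a zero share nothing changes. The figures assume exactly 10 prospective and 40 retrospective patients, and that every patient responds. The pooled SVR12 estimate remains a valid description of sofosbuvir-based therapy. What the plan as written cannot deliver is support for the ribavirin-free and FDC statements in 4.1.

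**What to change.** 1. Reword the first reason and the FDC sentence in 4.1. Let n = 50 support sofosbuvir-based therapy overall, and confine the ribavirin-free and FDC claims to patients confirmed to have had that regimen.
2. Confirm that DAA regimen and ribavirin or interferon use are abstracted for the retrospective arm, and list them in 11.2 or in the abstraction form.
3. Report SVR12 with exact intervals by regimen and by ribavirin use. Report retrospective-arm anemia and discontinuation by ribavirin use. Keep all of this descriptive, without tests between subgroups.

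The cost is two reworded sentences, at most a few abstraction fields and a small set of split tables. The downside is wider intervals in small subgroups, more so if they are also divided into pre- and post-transplant. The pooled analysis for objective 1 is unaffected.

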4.1.3 Safety Endpoints

The primary safety endpoint is any AE leading to permanent discontinuation of study drug(s).

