10.5 Reporting Procedures: Prospective Arm

10.5.1 Adverse Events

Throughout the study, the investigator must record all grade 3 or higher events based on the “Division Of AIDS Table For Grading The Severity Of Adult And Pediatric Adverse Events” (Version 2.0, November 2014), not present at baseline, on the appropriate Adverse Event Form within 5 business days of identification of the event. If an event is present at baseline, is clearly documented, and does not change in severity throughout the study, it does not need to be captured on an Adverse Event Form. However, if the event resolves, or begins to resolve, and then worsens again to a grade 3 or higher, it must be captured on an Adverse Event Form.

Within 5 business days of recognition of an adverse event, the Study Coordinator or site investigator will:

- Complete an Adverse Event Form in the RedCap Database.
- Record information on the adverse event in the participant's medical chart.
- Provide follow-up information when it becomes available

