10.6 Reporting Procedures: Retrospective Arm

Adverse event and safety monitoring is not required for the retrospective arm since the retrospective arm only involves data collection and elastography for those who consent. Elastography is ultrasound based and is without adverse events. However, sites will be asked to record data on historical adverse events identified in the medical record for data analysis (hospitalizations during treatment with DAA therapy, anemia requiring transfusion or EPO during treatment with DAA therapy, and death) but the retrospective arm participants are exempt from ongoing safety monitoring.

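### Section 4.1 applies n=50 to any type of adverse event, but for some events, including deaths in the first 12 weeks, only the 10 to 20 prospective patients are assured

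*Combined protocol and SAP*

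**What the plan says.** Reason 2 of section 4.1 holds that "A sample size of 50 (pre and post-transplant) is sufficient to address the safety endpoints". The note to Table 2 gives the chance of "observing at least 1 participant with the AE among 50 total participants": 39%, 92%, 99.5% and 99.97% at true rates of .01, .05, .10 and .15. From the 92% the section infers that "if no one has a given type of AE, we can be confident that its true probability is under 5" percent. Section 4.1.3 adds: "The primary safety endpoint is any AE leading to permanent discontinuation of study drug(s").

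The 50 are 10 (up to 20) prospective patients and 40 or more retrospective ones (Protocol Summary, section 3.0). The two arms record safety differently:

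- **Prospective.** Under section 10.5, headed for this arm, "the investigator must record all grade 3 or higher events". Section 8.8, also in a section headed for this arm, requires the reason for any discontinuation.
- **Retrospective.** Section 10.6: "Adverse event and safety monitoring is not required for the retrospective arm since the retrospective arm only involves data collection". It asks sites for historical events, listed as "hospitalizations during treatment with DAA therapy, anemia requiring transfusion or EPO during treatment with DAA therapy, and death". Section 3.1 adds discontinuation rates, without cause, and survival. It also says in general terms that the data will mirror those of the prospective arm.
- **Retrospective eligibility.** In section 5.1 both strata, candidates and recipients, require survival for at least 12 weeks from the start of treatment.

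**The concern.** The sample-size statement covers any type of adverse event, but a patient can count in the denominator only if the event could have been observed and recorded in that patient. For the retrospective arm two things stand in the way: a narrower set of recorded events, and an entry rule that makes early deaths impossible. With a 12-week course, the excluded period is the whole of treatment.

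If zero events of such a type are read against 50, the result will look far more reassuring than the data allow. Section 1.1 itself says that the safety of SOF/LDV has not been established in decompensated cirrhosis, so the safety statement matters here.

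**Working it through.** **1. Reproduce Table 2.** The chance of at least one event is 1 − (1 − p)^n. With n = 50 it is 39.5%, 92.3%, 99.5% and 99.97% at p = .01, .05, .10 and .15. The printed figures are confirmed.

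**2. Which events have which denominator.**

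| Event | Prospective (10–20) | Retrospective (40+) | Assured n |
|---|---|---|---|
| Hospitalization; anemia with transfusion or EPO | recorded | named in 10.6 | 50 or more, retrospective part among 12-week survivors |
| Discontinuation, any cause | recorded (8.8) | named in 3.1 | 50 or more, same condition |
| Discontinuation caused by an AE (primary safety endpoint) | reason recorded (8.8) | cause not expressly required | 10–20 assured, 50 possible |
| Other AE types, grade 3 or higher | recorded (10.5.1) | not named | 10–20 |
| Death in weeks 0–12 | observable | impossible by 5.1 | 10–20 |

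Early deaths can be seen in the prospective arm because section 5.2 sets only an expectation for survival (post-transplant stratum), not a realised survival time.

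**3. Detection chance at n = 10 and 20.**

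| n | p = .01 | .05 | .10 | .15 |
|---|---|---|---|---|
| 10 | 9.6% | 40.1% | 65.1% | 80.3% |
| 20 | 18.2% | 64.2% | 87.8% | 96.1% |
| 50 | 39.5% | 92.3% | 99.5% | 99.97% |

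**4. What zero events would show.** The two-sided 95% exact upper limit is 1 − 0.025^(1/n): 30.8% (n = 10), 16.8% (n = 20), 7.1% (n = 50). The last matches Table 1, where 50 of 50 gives a lower limit of 0.929, and 1 − 0.929 = 0.071. At the plan's own level (0.95^50 = 0.0769, so 92.3% one-sided) the limit is 1 − 0.0769^(1/n): 22.6% (n = 10), 12.0% (n = 20) and 5.0% (n = 50).

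**5. Range for the primary safety endpoint.** The documents do not say how many retrospective charts will hold a usable reason for stopping. The number of usable charts below is therefore an assumption, taken out of 40. Since the arm is 40 or more, 60 is not a ceiling.

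| Usable charts of 40 | n | Chance of at least one event at 5% | Two-sided limit after zero events |
|---|---|---|---|
| 0 | 10–20 | 40.1%–64.2% | 30.8%–16.8% |
| 20 | 30–40 | 78.5%–87.1% | 11.6%–8.8% |
| 40 | 50–60 | 92.3%–95.4% | 7.1%–6.0% |

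**6. Effect on SVR12.** A patient who dies within 12 weeks of starting can hardly have an HCV RNA value 12 weeks after treatment ends, and section 4.3 scores such missing values as failures. The survival criterion therefore removes likely failures from the retrospective arm. The documents give no number of early deaths, so only the direction can be stated: upward.

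**The case against.** The strongest reply is that the protocol intends fuller collection than section 10.6 suggests. Section 3.1 lists discontinuation under safety and tolerability and says that retrospective data will mirror prospective data, and prospective reasons are recorded. Section 10.2, which names no arm, says that grade 3 or higher events are recorded. The study is described as preliminary, has no safety test, and no analysis is specified that reads a zero count against 50.

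Part of this stands. A reader might infer that AE-caused discontinuation is excluded for retrospective patients. The documents do not say so: they are unclear, and the data forms cannot be seen. Nor is the list in 10.6 exhaustive, since 3.1 adds discontinuation. The lack of an AE row in the retrospective schedule (11.2) proves little: the prospective schedule (11.1) has none either, and 11.2 also omits the events that 10.6 does request. Section 9 says that enrolled patients given SOF/LDV will be evaluated for safety; it does not say that nobody else will be.

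It might also seem that the under-5% sentence fails because reason 1 works at 95% ("we can be 95% confident that the true SVR probability is between 0.929 and 1"). But the 92% is printed just before it and no 95% level is claimed for adverse events, so that is a matter of preference.

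What the reply does not meet is the specific waiver in 10.6, which displaces the general statement in 10.2 for this arm, and the survival criterion, which leaves no room for interpretation.

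**Conclusion.** The point holds as a mismatch between the stated denominator and what the design collects. For grade 3 or higher event types outside the retrospective list, and for deaths in the first 12 weeks, the assured n is 10 to 20, and the stated 92% becomes 40.1% to 64.2%. This rests on reading 10.6 as overriding 10.2, and for early deaths only on section 5.1.

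For the primary safety endpoint the conclusion is weaker, and confidence moderate: n = 50 is not assured, but it is not ruled out. For types below grade 3 even 10 to 20 is not assured, because the adverse event form is required only from grade 3.

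Table 2 is arithmetically right, and 50 remains usable for events recorded in both arms, provided the 12-week survival condition is stated. It would be wrong to infer that efficacy is untouched: Table 1's arithmetic stands, but the same criterion tends to raise the retrospective SVR12 rate by an amount the documents do not allow one to estimate.

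**What to change.** 1. Add a field to the retrospective abstraction (sections 10.6 and 11.2): reason for permanent DAA discontinuation, including adverse event.
2. In section 4.1, reason 2, limit n = 50 to events recorded in both arms: hospitalization, anemia with transfusion or EPO, all-cause discontinuation and, once abstracted, AE-caused discontinuation. State that retrospective safety data are conditional on 12-week survival, and do not use 50 for deaths in that period.
3. Add rows to Table 2 for grade 3 or higher event types captured only prospectively. At .01/.05/.10/.15 these are 10%/40%/65%/80% for n = 10 and 18%/64%/88%/96% for n = 20. Report every event type with its actual denominator.
4. Optional: replace the under-5% sentence with the zero-event limits for 0 of 50, which are 7.1% two-sided and 5.8% one-sided (1 − 0.05^(1/50)).

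The cost is some rewording, two table rows and one chart field. The reason for stopping may be missing in some records; those patients then count only for all-cause discontinuation. The stated safety figures become less favourable. The sample size does not change.

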ANC	absolute neutrophil count
AUC	Area under the curve
BMI	Body mass index
CHC	Chronic hepatitis C
DAA	Direct acting antiviral
ECG	Electrocardiogram
ESA	Erythropoiesis stimulating agent
ETR	end of treatment response: <LLOQ HCV RNA at the end of treatment
EVR	early virologic response: <LLOQ HCV RNA or 2-log decline at Week 12 (partial EVR)
FDA	Food and Drug Administration
FDC	Fixed dose combination
G-CSF	granulocyte colony stimulating factor
GT-1, -2, and -3	Genotype 1, 2, and 3
HBV	hepatitis B virus
HCV	hepatitis C virus
Hgb	hemoglobin
HIV	human immunodeficiency virus
IL28B	Interleukin 28B
IFN	interferon
IRB	Institutional Review Board
ISG	interferon-stimulated gene
LDV	Ledipasvir
LI	Lead investigator
LOD	Level of detection
LLOQ	Lower Level of quantification
MELD	Model for End-Stage Liver Disease
NIAID	National Institute of Allergy and Infectious Diseases
NIH	National Institutes of Health
PBMC	peripheral blood mononuclear cell
pegIFN	Pegylated Interferon
PI	principal investigator
sofosbuvir	sofosbuvir
QWBA	quantitative whole-body autoradiography
RBV	ribavirin
RVR	Rapid virologic response; <LLOQ HCV RNA at Week 4
SAE	Serious adverse events
SOC	Standard of care
SOF	Sofosbuvir
SVR	sustained virologic response <LLOQ HCV RNA at 24 weeks (or 6 months) after the end of treatment
TVR	Telaprevir

PROTOCOL SUMMARY

Full Title:	A Retrospective/Prospective Cohort Study to Assess Safety, Tolerability, and Efficacy of Sofosbuvir based Direct Acting Antiviral (DAA) therapy for Hepatitis C Treatment in HIV/HCV Coinfected Subjects Pre or Post Liver Transplant
Short Title:	Sofosbuvir based DAA therapy in HIV/HCV coinfected pre or post liver transplant
Study Name:	STOP-CO
DAIDS ES #:	12044
Clinical Phase:	Phase IV
Sample Size:	10+ prospective (up to 20) 40+ retrospective
Accrual Period:	12 months
Study Population:	HIV+ Adults with decompensated liver disease pre or post liver transplant with chronic hepatitis C virus (HCV) infection
Participating Sites:	Enrolling Centers: University of California, San Francisco, Mt. Sinai Medical Center, Columbia University, and University of Pennsylvania, University of Maryland, Georgetown University, Johns Hopkins University; Collaborating Center: NIH Clinical Center.
Study Design:	Retrospective/Prospective, open-label study using sofosbuvir based DAA therapy to treat HIV/HCV coinfected pre or post liver transplant participants

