4.4 Efficacy Analyses

4.4.1 Primary Analysis

The primary efficacy endpoint is SVR₁₂ (HCV RNA <LLOQ 12 weeks after cessation of therapy.)

There is no active comparator group for this study (as in most clinical trials with all oral therapies in these populations).

In the primary efficacy analysis, an exact Clopper-Pearson 95% confidence interval will be computed for the SVR₁₂ rate.

The primary analysis will be performed after all enrolled subjects have been followed through 12 weeks post-treatment or discontinued from study.

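### Zero events in 50 supports an AE probability under 5% only at about 92% one-sided confidence; the exact one-sided 95% upper limit is 5.8%

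*Combined protocol and SAP*

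**What the plan says.** Section 4.1 (Sample Size Requirements) gives three reasons for the total of 50. The second is safety: "A sample size of 50 (pre and post-transplant) is sufficient to address the safety endpoints". The support offered is a detection probability: "If the true event probability is 5% or more, there is about a 92% chance of observing at least one such adverse event". Table 2 tabulates the same quantity for four event rates; its note explains that "row 2 gives the probabilities of observing at least 1 participant with the AE among 50 total participants". From the 92% the section then concludes that "if no one has a given type of AE, we can be confident that its true probability is under 5" percent. No confidence level is attached to that conclusion.

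The efficacy reason in the same section does state its level: "if all 50 subjects have sustained virologic response, we can be 95% confident that the true SVR probability is between 0.929 and 1". Section 4.4.1 names the matching method: "an exact Clopper-Pearson 95% confidence interval will be computed for the SVR₁₂ rate". The Protocol Summary breaks the sample down as "10+ prospective (up to 20) 40+ retrospective".

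**The concern.** The safety sentence turns a probability of seeing an event into a confidence bound without saying how much confidence the bound carries. A reader who has just met 95% in the efficacy paragraph will tend to carry that level over, and at 95% the bound does not hold for 50 participants by the exact method.

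What is at stake is how a clean result for some AE would be read. The sentence supports the claim that 50 is enough for safety, and safety and tolerability of SOF/LDV is a primary endpoint (Section 3.3.1). The next sentence in Section 4.1 moves to evidence on the fixed-dose combination, so a reader could also apply a bound derived for 50 to the much smaller prospective arm.

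**Working it through.** **Inputs.** n = 50, zero events, a 5% threshold and a stated detection probability of about 92% (all Section 4.1); 95% as the efficacy level (Sections 4.1 and 4.4.1); 10 to 20 prospective participants (Protocol Summary and Section 3.0).

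**1. Reproduce Table 2.** The probability of at least one event is 1 − (1 − p)^50.

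| True rate p | Computed | Stated |
|---|---|---|
| 1% | 39.499% | 39% |
| 5% | 92.3% | 92% |
| 10% | 99.48% | 99.5% |
| 15% | 99.97% | 99.97% |

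Every entry agrees. The Table 1 intervals also reproduce as exact two-sided 95% limits with n = 50.

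**2. Confidence carried by the 5% bound.** If p = 5%, the chance of zero events in 50 is 0.95^50 = 7.7%. Seeing 0/50 therefore excludes rates of 5% or more with 1 − 0.077 = 92.3% one-sided confidence. Since 7.7% exceeds 5%, a rate of 5% is not excluded at the 95% level.

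**3. Exact 95% upper limit for 0/n.** Solve (1 − p)^n = a, so p = 1 − a^(1/n), with a = 0.05 one-sided or 0.025 two-sided.

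| n | One-sided 95% | Two-sided 95% | Chance of at least one event at p = 5% |
|---|---|---|---|
| 50 | 5.8% | 7.1% | 92.3% |
| 20 | 13.9% | 16.8% | 64.2% |
| 10 | 25.9% | 30.8% | 40.1% |

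The 7.1% mirrors the protocol's own efficacy figure: 1 − 0.929 = 0.071.

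**4. Size at which the bound would hold at 95%.** One-sided: ln 0.05 / ln 0.95 = 58.4, so n = 59. Two-sided: ln 0.025 / ln 0.95 = 71.9, so n = 72.

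**5. Sensitivity to method, 0/50.** Rule of three: 6.0%. Wilson: 5.1% one-sided, 7.1% two-sided. Mid-P: 4.5% one-sided, 5.8% two-sided. Jeffreys: 3.8% one-sided, 4.9% two-sided.

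**The case against.** The strongest reply is that the protocol never claims 95% for this sentence. It says only that one can be confident, it draws the conclusion directly from the 92% given just before, and at 92.3% one-sided the conclusion is true. This stands. A reader might infer that the safety arithmetic is wrong; the documents do not support that, because every Table 2 entry is correct. The fault is an unstated level lower than the one used beside it.

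Second, an upper bound on a rate is a one-sided statement, and Section 4.4.1 assigns the two-sided Clopper-Pearson interval to SVR₁₂ only; Section 4.5 gives no interval for adverse events. This also stands. The natural comparator is 5.8%, and 7.1% is useful only to show the scale used for efficacy. Some less conservative methods fall below 5%, so the result is specific to exact limits, the only kind the protocol names.

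Third, the plan allows 20 + 40 = 60 participants, and at 60 the exact one-sided limit is 1 − 0.05^(1/60) = 4.9%. That shows how narrow the margin is. It does not rescue a sentence written for 50, and Section 3.0 expects approximately fifty.

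Fourth, a reader might infer that only 10 to 20 participants in the whole study received SOF/LDV, so that the far wider limits apply to the drug. The documents do not support that. The retrospective arm takes patients on any sofosbuvir-based regimen since January 2014, and Section 1.1 dates approval of the combination to October 2014. Some retrospective patients may have taken it; how many is not stated.

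**Conclusion.** The point holds as a matter of an unstated and lower confidence level. With no events in 50, the 5% bound carries 92.3% one-sided confidence; at 95% the exact one-sided limit is 5.8%, which is 0.8 percentage points higher. The two-sided figure is 7.1%.

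The practical consequence is small. There is no safety hypothesis test, the numerical criterion for pausing enrolment (Section 16.1.1) concerns treatment failure, and Section 4.1 itself calls the evidence preliminary. The sentence is still worth correcting because it is a stated ground for the adequacy of the sample.

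The figures assume independent participants with a common event probability, all 50 assessed for the AE in question, and exact binomial limits. The limits for 10 and 20 describe the prospective arm only and must not be read as limits for everyone in the study who received SOF/LDV.

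**What to change.** In Section 4.1, remove the under-5% bound and replace the sentence with wording such as:

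> If none of 50 participants has a given AE, the exact one-sided 95% upper limit for its probability is 5.8% (7.1% as the upper end of a two-sided 95% Clopper-Pearson interval).

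Leave Table 2 as it is. If the authors prefer to keep the 5% figure, the least they should do is state that it carries about 92% one-sided confidence.

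If a statement is wanted for the prospective SOF/LDV arm, add one labelled as prospective arm only: with zero events, the exact 95% upper limit is 25.9% for 10 participants and 13.9% for 20, one-sided (30.8% and 16.8% two-sided).

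The cost is one or two sentences and a slightly less favourable bound. Design, sample size and analyses are unchanged.
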